6.7. Power. Stroup¹⁰¹ (also see Littell et al.¹⁰²) has outlined a four-step procedure to estimate power for general linear mixed models, which can also be applied to generalized linear mixed models as occur in the proposed study. This procedure was implemented in the current case. For each of the number of Times outcomes were measured (4, 5, 6, 7, or 9), three datasets for each hypothesis were created, assuming the dependent variable was continuous and normally distributed, discrete and Poisson distributed, or dichotomous and binomially distributed. For the normally distributed case, the only non-null effect in the model was the hypothesized effect of interest, with the XR-NTX-OTx condition mean set at 1 at Time 1, decreasing by .1 at each subsequent Time point, while the XR-NTX+MMTx condition means were set at 1 at Time 1, and then adjusted to reflect “small”¹⁰³ mean differences (.2 of the standard deviation at subsequent Time points) consistent with the hypothesis of interest. [Time was not included in the estimation of power for the criminal justice outcomes because these outcomes are measured only at 12-month post-baseline assessment.] Similar specifications were made for the datasets with outcomes following the Poisson and binomial distributions. Finally, observations were dropped from the data consistent with the expected loss of approximately 10% of participants at the 12-month assessment (see **Participant Attrition**, above). Hence, power was estimated for a design in which the effects were unbalanced in a manner similar to what was expected to occur in the proposed research. Therefore, simulations were conducted under what might be considered “worst-case scenarios.” Power was then estimated for three different covariance structures (compound symmetric heterogeneous, first-order autoregressive heterogeneous, and unstructured) of the observations over Time. [Covariance structures can be specified for GLiMM models independent of the location (e.g., mean) structure, so it was only necessary to create a single dataset for the three cases.] Assuming a sample size of 240 and $\alpha=.05$, the resulting power values ($1 - \beta$) for the Treatment Condition X Time effect varying between .81 and .85 in the simulations. From a more rudimentary and slightly less accurate perspective, assuming the primary outcome measures follow a normal distribution rather than binomial or Poisson distributions, power calculations based on the set correlation method¹⁰⁴ can be used to calculate effect sizes for desired power, including under the extremely conservative assumption that no other effect in the model is significant (with the resulting effect size estimates likely to be slight underestimates). In this case, assuming $\alpha=.05$ and $N=216$ due to attrition (see **Participant Attrition**, above) in order to remain conservative, an effect size of $f^2=.037$ in the population associated with a Treatment Condition main effect for statistical models in which there is no Time effect (e.g., reincarceration) and effect sizes ranging from a minimum $f^2=.046$ to a maximum $f^2=.072$ for the Treatment Condition X Time effects associated with the 4, 5, 6, 7, or 9 Time points for statistical models in which there is a Time effect, would yield a power of .8 for the respective effect. These effect sizes fall toward the “small-to-medium” range, with $f^2=.02$ considered a “small” effect and $f^2 = .15$ a “medium” effect.¹⁰³ In other words, and imprecisely, under the assumption that the effect in the population was $\geq .037$ or $\geq .072$, for the Treatment Condition and Treatment Condition X Time effects, respectively, there is an 80% chance of concluding that effect is significant if α is set to .05 and 216 participants are assessed at 12-month follow-up. *Power calculations do not utilize any estimates of treatment efficacy from prior studies. This latter approach to power analysis, although once popular, is often quite limited, as is the case for the proposed study, in that prior studies may have examined populations that are not comparable to the population in the proposed study and/or do not include the same experimental or control conditions, and in all cases, the effect sizes reported in prior studies are generally subject to wide fluctuation due to sampling variability.*¹⁰⁵ Power was calculated to detect a stated effect size, as detailed in the proposal, an approach consonant with more recent writings regarding power analysis.

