
6.8. Supplementary Analyses. We will tabulate (and test for treatment condition differences) for the relative frequency of each adverse event (AE) in each condition, where the examination is based on the proportion of

individuals who experience the AE, and the number of that AE reported. In addition, we will tabulate and test for treatment condition differences) for the relative frequency of opioid overdoses in each condition, where the examination is based on the proportion of individuals who report overdoses during the 12-months post-release. We will also calculate mean scores of cravings at each follow-up.

6.9. Additional Process Data *We will collect three additional process variables: (1) data on housing stability at each follow-up visit that will utilize a checklist to describe the participant's place of residence and the level of stability; (2) data on the distance travelled from place of residence to Glenwood Life Counseling Center (GLC) for participants randomized to TAU; and (3) data on the number of counseling sessions received during the course of the study (this will account for any community counseling received during treatment).*

6.10. Follow-up Analyses. *Follow-up analyses will include select covariates in the model, with a focus on the covariate X BI Intervention Condition (X Time, if an outcome is measured repeatedly). These follow-up analyses can be viewed as either sensitivity analyses or as subgroup analyses^{106,107} intended to map the population(s) for which the intervention is maximally useful and/or examine the robustness of the findings under uncertainty in the model. Possible covariates include: (1) crime severity, (2) opioid severity, (3) housing stability, (4) distance travelled from place of residence to treatment clinic; and (5) number of counseling sessions received.*

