7.0. Project Timeline

Months 1-5 will be devoted to start-up activities, including confirming logistic arrangements, recruiting and training staff, and developing detailed procedures with prison and treatment personnel, and obtaining IRB and OHRP approval. Recruitment of participants and delivery of interventions will begin in month 6. Five to six prison inmate/participants are projected to be enrolled per month, yielding a total of 240 participants (120 per condition), at the end of recruitment (month 40). Follow-up assessments will be completed by month 53. Months 54-60 will be devoted to dissemination activities (e.g., publication of the primary outcomes paper).

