9.2. Protection Against Risks

9.2.1. Risks Associated with XR-NTX. Participants may experience symptoms of opioid withdrawal from the naloxone challenge, oral naltrexone, or XR-NTX injection. In order to minimize the likelihood of withdrawal symptoms, potential participants will be carefully screened with exclusion criteria which include recent opiate use history and a urine test prior to naloxone administration. The study design was carefully crafted to minimize risk of withdrawal by first administering the short-acting naloxone followed by a small oral dose of naltrexone prior to XR-NTX administration. Individuals who do experience opiate withdrawal symptoms from the administered opioid antagonists will be treated symptomatically by the study’s medical personnel.

To protect against risks of increase in liver enzymes, study applicants will be excluded if their liver enzymes are greater than triple the normal levels. Also, liver enzyme tests will be repeated during the course of the study and doses withheld if indicated.

Participants will be warned of the risk of opioid overdose should they discontinue XR-NTX and will be informed of alternative treatment, including methadone or buprenorphine treatment. Finally, participants will be informed that they should carry their study identification card with them and provide it to any medical personnel that will be treating them in the future so they can be aware of the need to provide appropriate alternatives to opioids for pain relief.

The study physician has extensive experience in the injection technique. This should minimize the likelihood of injection site reactions. Nonetheless, the FDA has provided the following information for healthcare professionals with regard to Naltrexone Injection Site Reaction [naltrexone for extended-release injectable suspension (marketed as Vivitrol)] FDA Alert [08/12/08] Vivitrol injections may be followed by pain, redness, itching, bruising, and swelling. Sometimes reactions at the injection site can quickly worsen and skin and other tissue can be permanently damaged and require surgery. If an injection site reaction does not improve within two weeks following the injection, or it worsens sooner than 2 weeks, the participant will be instructed to see his/her doctor. The dose of Vivitrol® (380mg) selected for this research has been studied in both normal healthy adults as well as in individuals who were using opioids, alcohol, and stimulants.

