9.8. Adverse Event Reporting

As in our other clinical trials, adverse event reporting will follow the usual FRI policy. Serious adverse events (SAEs) include any of the following outcomes for the participant: 1) death; 2) acute life-threatening incidents; 3) hospitalization or the prolongation of a hospitalization; 4) persistent or significant disability or incapacity; or, 5) birth defects. Should they occur, these events may be communicated to the PI by participants and/or staff, or may be observed directly by the PI. SAEs will be reported regardless of whether they are considered study related. Adverse events will be monitored by nursing and medical staff and will include: nasopharyngitis, insomnia, and injection site pain among other more frequently reported reactions. The completed Serious Adverse Event Form will contain: subject's ID#, gender, age, the title and date of the Serious Adverse Event, and narrative explanation. The Serious Adverse Event Report Form tracks how the research staff was notified of the event, dates of consent, study medication, study screening for inclusion/exclusion, study treatment received, outcome of study treatment (e.g., was participant using illicit substances or abstinent, other relevant clinical information), dates and circumstances of the hospitalization/death, whether alcohol or illicit substances were known to be involved, and participant status at last clinical or research contact. In cases of participant death, the report also includes appropriate substantiation from clinic records, as well as copies of the death certificate, autopsy report, or medical record. The Principal Investigator will address whether there is a need to redesign or amend the protocol, and/or to inform current and future subjects of a change in description of risk (in consent form and protocol or other). The Principal Investigator will state whether the event was "expected" and assess its "relatedness" to the study medication or intervention.

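### Section 6.8 tests each adverse event separately on two measures, with no multiplicity rule and no arm comparison of any injection-site reaction or any SAE as a class

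*Combined protocol and SAP*

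**What the plan says.** Section 6.8 (Supplementary Analyses) tabulates adverse events by condition and tests for arm differences "for the relative frequency of each adverse event (AE) in each condition". Each event is examined in two ways, "where the examination is based on the proportion of" "individuals who experience the AE, and the number of that AE reported". Opioid overdose has its own comparison, on the proportion reporting one over 12 months. Section 6.8 plans no other arm test of safety. It names no coding level, grouping, minimum frequency, alpha or multiplicity rule for these tests.

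Elsewhere the protocol describes events that belong together. Section 9.2.1 reports that "Vivitrol injections may be followed by pain, redness, itching, bruising, and swelling", and Section 9.2.2 adds severe signs such as hardness, an open wound, a dark scab, lumps and blisters. Section 9.8 defines serious events as a class ("Serious adverse events (SAEs) include any of the following outcomes for the participant") and names injection-site pain as an adverse event in its own right. Section 5.6.2, by contrast, refers to an injection site reaction as one thing.

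**The concern.** Both arms receive the same drug. What is randomized is where the post-release injections are given, so injection-site harm is a natural safety question for home delivery. If its signs are counted as separate terms, a shared excess is spread over several small comparisons, none with much power. At the same time, many unadjusted tests on two measures can produce chance flags among the commoner terms. No planned comparison answers the simpler question of whether more people in one arm had any injection-site reaction, or any SAE. A grouping chosen after arm-level results have been seen would be open to challenge.

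**Working it through.** **Inputs from the plan.** Section 7.0 gives the sample size, "yielding a total of 240 participants (120 per condition"). Section 6.7 uses alpha 0.05, and N = 216 after attrition. These reproduce the plan's own detectable effect: f² = 0.037, u = 1, v = 214, noncentrality 0.037 × 216 = 7.99, power 0.80; and 216 / (1 − 0.10) = 240. The plan gives no power or error rate for the adverse-event tests.

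**Assumptions.** All event rates, the number of terms, two-sided 0.05 per test, and the test itself. Section 6.8 names no test, so Fisher's exact and the uncorrected chi-square are shown as a range.

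**1. Rare terms.** With 120 per arm and all k affected people in one arm, Fisher's two-sided p = 2 × C(120,k) / C(240,k).
- 5 v. 0: p = 0.060
- 6 v. 0: p = 0.029

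Under Fisher, a term seen in five or fewer people cannot reach 0.05. The uncorrected chi-square reaches it at 4 v. 0.

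**2. One term against one pooled class.** Power = Σ Bin(x; 120, p₁) × Bin(y; 120, p₂) over all outcomes (x, y) with p < 0.05. Take any injection-site reaction in 10% v. 22%, divided evenly over five signs.

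| Comparison | Fisher | Chi-square |
|---|---|---|
| One sign, 2.0% v. 4.4% | 0.085 | 0.162 |
| Pooled, 10% v. 22% | 0.665 | 0.733 |

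**3. Five term tests held to a 5% family error rate.** Each is tested at 0.05 / 5 = 0.01. With one sign per affected person, per-term power is 0.024 (Fisher) or 0.045 (chi-square). Treating terms as independent, the chance of at least one flag is 1 − (1 − 0.024)⁵ = 0.11 or 1 − (1 − 0.045)⁵ = 0.21. Simulation, letting each affected person have one, two or three of the five signs, gives 0.12 to 0.49 (Fisher) and 0.21 to 0.59 (chi-square); a rerun agreed to about 0.01. The pooled test is ahead in every case.

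**4. Other rates (Fisher).** Per-term rates are held fixed; the pooled range runs from heavy overlap between signs (correlation 0.8) to none.

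| Each of five terms | One term | Pooled |
|---|---|---|
| 1% v. 2% | 0.01 | 0.08 to 0.20 |
| 2% v. 4% | 0.06 | 0.17 to 0.43 |
| 2% v. 5% | 0.13 | 0.34 to 0.74 |

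**5. Where pooling loses.** Only one sign rises, 2% to 10%, and four stay at 2%. The pooled rates, for independent signs, are 1 − 0.98⁵ = 9.6% and 1 − 0.98⁴ × 0.90 = 17.0%. Fisher power is 0.68 for the single term (0.45 at alpha 0.01) and 0.32 for the pooled class.

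**6. Chance flags, proportion measure only, no true difference, terms at 2-15%.** The true error rate per test averages about 0.025 (Fisher) and 0.050 (chi-square), and the chance of any flag is 1 − (1 − rate)ᵏ.

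| Terms | Fisher | Chi-square |
|---|---|---|
| 5 | 0.12 | 0.23 |
| 10 | 0.22 | 0.40 |
| 20 | 0.40 | 0.64 |
| 30 | 0.53 | 0.78 |

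Simulation gives 0.12 to 0.40 for 5-10 terms and 0.39 to 0.79 for 20-30. Adding the count measure raises these. With terms at 1-20%, Fisher for incidence and a conditional Poisson test for counts, the chance of a flag on either measure is 0.15 to 0.26 for 5 terms, 0.27 to 0.45 for 10, 0.47 to 0.70 for 20 and 0.62 to 0.84 for 30.

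**The case against.** The strongest reply is that the splitting is inferred. The lists in Sections 9.2.1 and 9.2.2 are warning text, not a coding scheme, and Section 5.6.2 treats the reaction as one event. If it is counted that way, the power loss for injection-site harm disappears. This stands in part: the counting level is unspecified, Section 9.8 points towards separate terms, and the missing any-SAE comparison remains either way.

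A reader might infer that a real excess would mostly be missed. The documents do not support that. With 10% v. 22% overall, the chance that at least one of five unadjusted term tests flags is 0.36 (Fisher) to 0.59 (chi-square) with one sign per person, 0.66 to 0.81 with two, and 0.76 to 0.85 with three. The cost is a family error rate that the plan does not control.

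A reader might also infer that chance flags are likely. That needs about 20 or more terms including fairly common ones, and the plan gives no count. The two problems fall mostly on different terms: under Fisher, the error rate per test is about 0.1% at 1% incidence and 0.7% at 2%.

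Safeguards exist. Section 6.1 intends confidence intervals and effect sizes, Section 9.12 has the DSMB review all SAEs, and stopping for safety (Section 9.13.1) rests on number and severity. Section 5.7.2 applies the clinic procedures at home. Section 6.5 assigns GLiMM to all analyses, so the Fisher threshold is illustrative. None of these creates a pooled comparison by arm.

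Finally, Sections 5.9.2 and 5.9.3 expect better adherence in the mobile arm, hence more injections. A per-person excess could then reflect exposure alone. This stands, and the fix has to meet it.

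**Conclusion.** The concern holds in a limited form. Section 6.8 tests each adverse event on two measures without a multiplicity rule and plans no arm comparison of injection-site reactions or SAEs as a class. If related signs are counted separately at a few percent each and rise together, one pooled test has clearly more power than term tests held to the same error rate: 0.67 to 0.73 against 0.12 to 0.59 in the example.

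It would go too far to say that pooling would detect the harm. Power falls to 0.34 with heavy overlap at 2% v. 5% per term, is lower still for smaller excesses, and drops below that of the single term when one sign alone rises. All rates and term counts are assumptions. Aims 1 and 2 are unaffected. This is a change to consider.

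**What to change.** In Section 6.8:

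- State the level at which an adverse event is counted.
- Name two or three pooled arm comparisons: any injection-site reaction; any SAE; and, optionally, any opioid-withdrawal event after a study antagonist. For each, make the proportion of participants the one main measure, with a difference, 95% CI and test.
- Also report injection-site reactions per injection given, because the arms may differ in the number of injections.
- Fix the grouping of terms before any arm-level adverse-event comparison is made. No blinding is described, so there is no unblinding date to tie this to.
- Keep the individual-term table descriptive, with differences and CIs and no significance tests.

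The cost is wording and one list of grouped terms; no new data are needed. The downside is that a pooled class mixes mild and severe events and dilutes a rise in a single sign, so the term table must stay beside it.

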Objectives/Outcomes:	Aim 1. To compare the two study conditions in terms of: a) XR-NTX treatment adherence; b) opioid use; c) criminal activity; d) re-arrest; e) re-incarceration; and f) HIV risk-behaviors (i. needle use; and ii. risky sexual behaviors). Aim 2. To determine if the number of months of post-release XR-NTX treatment is related to outcomes (a-f above), and if so, is there a point at which XR-NTX v. Non-XR-NTX equilibrates. Such a finding could be potentially important because it would be informative about the needed length of XR-NTX treatment
Study Design:	The study is a parallel two-group randomized controlled trial in which 240 (120 per condition) incarcerated men and women will be randomly assigned within gender to one of two conditions: Condition 1. XR-NTX-OTx. One injection of XR-NTX in prison, followed by 6 monthly injections post-release at a community opioid treatment program. Condition 2. XR-NTX+ MMTx. One injection of XR-NTX in prison followed by 6 monthly injections post-release at the participant's place of residence utilizing mobile medical treatment. All participants will be evaluated at 1-, 2-, 3-, 4-, 5-, 6-, 7- (safety visit) and 12-months after release from prison.

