5.9. Study Aims, Hypothesis, Rationale

5.9.1. Aims. The proposed study has two specific aims: **Aim 1.** To compare the two study conditions in terms of: a) XR-NTX treatment adherence; b) opioid use; c) criminal activity; d) re-arrest; e) re-incarceration; and f) HIV risk-behaviors (i. needle use; ii. risky sexual behaviors). **Aim 2.** To determine if the number of months of post-release XR-NTX treatment is related to outcome (a-f above), and if so, is there a point at which XR-NTX v. Non-XR-NTX equilibrates.

5.9.2. Hypothesis. Based on data from the research team's current studies (see above), It is anticipated that the XR-NTX+MMTx condition will have superior outcomes compared to the XR-NTX+OTx condition in terms of outcomes (a)-(f).

5.9.3. Rationale. We are not aware of RCTs using mobile medical treatment for the provision of XR-NTX. However, based on studies utilizing mobile treatment for HIV services, and methadone, which increased access, engagement, and retention, we believe the provision of medical treatment, provided at a participant's place of residence, is expected to yield better adherence, subsequently, improving outcomes mentioned above. If we find a point of equilibration it will tell us how many months we will need to provide mobile treatment (XR-NTX) and at what point it impacts on outcomes-significant given the cost of the medication. It is difficult to provide firm conjectures on this latter question given the lack of research in this area.

Figure 2: Data Collection Schedule

Measures	Source	Interval	Operational Definition
Aim 1: Outcomes (a)-(f)			
a. XR-NTX adherence	Clinic records	B, 1-6	• # of injections due/completed
b. opioid use	ASI/TLFB/UDS	B, 1-6, 7, 12	• days of opioid use • positive opioid urine drug screen
c. criminal activity	ASI/TLFB	B, 1-6, 7,12	• days of crime
d. re-arrest	Official records	12	• time to re-arrest
e. re-incarceration	Official records	12	• time to re-incarceration
f. HIV risk behaviors	RAB/TLFB	B, 1-6, 7,12	• scored 0-22 (higher risk) • scored 0-18 (higher risk)
i. needle use			
ii. risky sex behaviors			
Aim 2: Outcomes (a)-(f)			
(a)-(f) equilibrates	Above	1-6,12	Time to relapse
Supplementary			
other treatment	ASI	B, 1-6, 7, 12	• Days in other treatment
opioid overdose	OOS	B, 1-6, 7, 12	• # of times overdosed
opioid craving	VAS	B, 1-6, 7, 12	• 0-100 (higher cravings)
Quality of Life	QOL	B, 1-6, 7, 12	

Figure 3: Biometric Measures

Measures	Data Collection Point						

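### For injection-related adverse events, the per-person arm comparison in 6.8 needs a per-injection companion, because the mobile arm is expected to receive more injections

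*Combined protocol and SAP*

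**What the plan says.** Section 6.8 will tabulate and "test for treatment condition differences) for the relative frequency of each adverse event (AE) in each condition". The two measures are the proportion of "individuals who experience the AE, and the number of that AE reported". No denominator of injections given is named there. Sections 6.3 to 6.5 supply no exposure offset, and injections received is not among the possible covariates in 6.10.

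The protocol expects the arms to differ in exposure. Section 5.9.2 states: "It is anticipated that the XR-NTX+MMTx condition will have superior outcomes compared to the XR-NTX+OTx condition in terms of outcomes (a)-(f"), and outcome (a) is XR-NTX adherence. Sections 5.9.3 and 8.0 repeat the expectation of better adherence with home delivery.

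Injection reactions are among the AEs counted. Section 9.8 lists "nasopharyngitis, insomnia, and injection site pain among other more frequently reported reactions", and sections 5.7.4 and 9.2.1 describe local reactions to the injection. Figure 2 (section 5.9) already collects the number of injections due and completed.

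**The concern.** Both arms receive the same drug at the same dose. They differ in where the community injections are given and, if the hypothesis is right, in how many are received. A local reaction can follow any injection, so an arm that receives more injections will tend to have more people with a reaction and more reactions in total, even if each home injection is exactly as safe as each clinic injection.

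The comparison in 6.8 therefore cannot say whether an excess in the mobile arm comes from the setting or from better adherence. The reverse can also happen. If mobile adherence were lower, a higher risk per home injection could go unseen: 3.26 injections at 12.5% risk and 4.07 injections at 10% risk both give 0.41 reactions per person.

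At stake is what can be said about injecting at the place of residence. Section 3.0 describes the trial as the first US randomised comparison of mobile with clinic XR-NTX, so readers are likely to look to it for that.

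**Working it through.** **The plan's own figure.** The plan gives no number for the AE comparison. Its nearest figure is for a between-arm efficacy effect, "assuming $\alpha=.05$ and $N=216$ due to attrition": f² = .037 for power .8. A noncentral F with 1 and 214 df and noncentrality .037 × 216 = 7.99 gives power .804, so that figure reproduces. Section 6.8 states no alpha or sidedness for the AE tests. I assume two-sided .05, so the nominal chance of a significant excess in the mobile arm is 2.5%.

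**Inputs from the documents.**
- Arm size: 120 (synopsis, Study Design).
- Clinic-arm exposure, with the pilot as proxy (section 2.7.3): 21, 18, 13, 11, 10 and 10 of 27 received community injections 1 to 6. The mean is 83/27 = 3.07, or 4.07 with the prison injection.

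**Assumptions.**
- Risk per injection q is the same in both arms, 1% to 15%.
- Mobile-arm mean M is 4.56, 5.0, 5.5 or 6.0 injections. The value 4.56 reads the small difference of .2 SD in section 6.7 onto total injections. With monotone dropout the pilot totals are 1, 2, 3, 4, 5 and 7 injections in 6, 3, 5, 2, 1 and 10 people. Their SD is √(610/27 − 4.07²) = 2.45, and 4.07 + .2 × 2.45 = 4.56.

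**Count comparison.** Expected events per person are λ = M × q. With n = 120 per arm, z = (λ_mobile − λ_clinic) / √[(λ_mobile + λ_clinic)/n], and the chance of a significant excess is Φ(z − 1.96). Example with M = 5.5 and q = 10%: λ = .550 v. .407, z = .143/√(.957/120) = 1.60, Φ(−.36) = 36%.

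| Mobile mean (ratio to 4.07) | q = 1% | 5% | 10% | 15% |
|---|---|---|---|---|
| 4.56 (1.12) | 4% | 6% | 8% | 10% |
| 5.0 (1.23) | 5% | 11% | 19% | 26% |
| 5.5 (1.35) | 7% | 20% | 36% | 50% |
| 6.0 (1.47) | 10% | 32% | 56% | 73% |

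Section 6.7 allows for an "expected loss of approximately 10% of participants at the 12-month assessment". With 108 per arm, z shrinks by √(108/120) = .949, and the worked example falls from 36% to 33%.

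**Proportion comparison.** I used the pilot's spread of injections for the clinic arm. For the mobile arm I used retention like that of the parolee study in section 1.0 (95%, 65% and 59% at injections 1, 5 and 6, interpolated linearly between the first and fifth; mean 5.59). The chance of a significant excess is 8% at q = 1%, 22% at 5% and 39% at 10%. At q = 10% the share with any reaction is 32.7% v. 43.2%.

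**Clustering.** With an assumed within-person correlation of 0.2, person-level variance and q of 5-15%, the count comparison gives 7-16% at 5.0 injections, 12-30% at 5.5 and 16-45% at 5.9.

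**Per-injection comparison.** Simulated trials with equally safe arms used events divided by injections received, with person-level robust variance. They showed a significant mobile-arm excess in 2.2-3.8% of trials. That simulation counted the prison injection. Restricting to community injections follows the same logic, since the expected rate ratio is again 1.

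**The case against.** The strongest reply is that nothing in 6.8 is wrong. Section 6.2 sets an intent-to-treat approach for all analyses. If mobile delivery leads to more injections and so to more reactions, that is a real consequence of assignment. No aim or hypothesis in 1.2 or 5.9 concerns safety per injection. A reader might infer that an excess in the mobile arm would be a false signal and that the per-person measure should go. The documents do not support that. The excess would be true of the strategy, and would mislead only if taken as evidence about the home setting.

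Four further points stand in part.
- **Inputs.** The risk per injection and the adherence gap are both assumed. At 1% risk, or with a small gap, the inflation is slight. Section 1.0 itself calls the parolee population more stable, so 6.0 injections is optimistic.
- **Scope.** A reader might extend the point to every AE. Section 9.8 also lists nasopharyngitis and insomnia, and nothing shows that these accrue per injection.
- **Setting.** The prison injection comes before any difference between arms. Section 5.7.2 applies the same procedures at home as at the clinic, and lets homeless participants be injected at the clinic or field office. An arm-level rate is therefore not a pure home-versus-clinic contrast.
- **Consequence.** These are supplementary analyses. A reader might infer that the 6.8 tests could stop the trial, but section 9.13.1 rests safety stopping on the monitoring board's judgement of the number and severity of study-related events.

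None of this supplies the missing information. Without a rate per injection, the planned tables cannot separate setting from exposure.

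**Conclusion.** The point holds as a gap in interpretation. Section 6.8 measures total AE burden by arm correctly, but for injection-related AEs it cannot separate the effect of home delivery from the effect of more injections. With equal risk per injection, every positive adherence gap examined raises the expected chance of a significant mobile-arm excess above the nominal 2.5%. The rise is to about 4-10% for a small gap and, at the extreme of 6.0 injections and 15% risk, to 73%.

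These figures rest on the pilot as proxy for the clinic arm, an assumed risk of 1-15%, an assumed mobile mean of 4.56 to 6.0 injections, and, for the tabulated values, independent events. Within-person clustering lowers them. They show what can happen and are not a forecast. The efficacy conclusions do not depend on this.

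**What to change.** Keep the per-person comparison in 6.8. For injection-related AEs only, such as injection-site reactions, add a between-arm comparison of events after community injections per community injection received:
- a count model with log(community injections received) as offset;
- person-level robust or over-dispersed variance, which section 6.3 already allows for counts. With clustered events, a mobile mean of 5.59 and 10% risk, a plain Poisson test of the per-person counts was significant in 43% of simulated trials, against 24% with person-level variance;
- the prison injection, and events following it, excluded.

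State in 6.8 that the two results are read together before any arm difference is attributed to the setting.

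The cost is one table and one model on counts already collected, provided that each event can be dated to the injection it followed. People with no community injection add neither events nor exposure. The downside is that injections received is determined after randomisation and people who react may stop, so the arms' later injections may be selected on tolerance. The rate is therefore supportive and descriptive, and should not be the sole basis for judging the safety of home injection.
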